10. STUDY CALENDAR

1 cycle = 2 treatments over 28 days (treatments are given every 2 weeks) D1=Day 1 D15=Day 15	Baseline ¹	Cycles 1-2		Surgical Evaluation/EOT ²	Long-term Follow-up ⁹ Post-neoadjuvant tx
	-28 days	Day of Cycle (± 7 days)		4 (+/- 2) weeks post neoadjuvant tx	
		D1	D15		
REQUIRED ASSESSMENTS					
Medical history	X				
Height	X				
Physical examination	X	X	X		
BP, weight	X	X	X		
ECOG performance status	X	X	X		
Complete metabolic panel	X	X	X		
Calculated creatinine clearance	X	X	X		
Platelets, ANC & Hgb	X	X	X		
CA 19-9	X				
Urine pregnancy ³	X				
AE and concomitant medication assessment	X	X	X	X ¹⁰	
Overall survival					X
Disease progression					X
DISEASE ASSESSMENT					
MRI or CT chest, abdomen, pelvis	X			X ⁵	X ⁴
Surgical resection (if applicable)				X	
TREATMENT					
Neoadjuvant FOLFIRINOX		X	X		
CORRELATIVE STUDIES					
Tissue collection	X ⁶			X	
Blood collection	X ⁶			X	
ASSESSMENTS					
PG-SGA questionnaire	X ⁷			X ⁸	
FAACT questionnaire	X ⁷			X ⁸	

Calendar Footnotes:

¹ Baseline assessments performed within 7 days of Cycle 1 Day 1 do not need to be repeated.

² All patients will have a surgical evaluation visit 4 (+/-2) weeks of completing or discontinuing neoadjuvant chemotherapy as part of their routine care. Information collected during this visit will be used for the EOT visit for this study.

³ Required only for women of child-bearing potential.

⁴ Disease progression will be assessed via radiology report from any MRI or CT scans done during the follow-up period per standard of care.

⁵ Repeat imaging may be performed prior to surgical resection at the treating physician's discretion.

⁶ Whenever possible

⁷ PG-SGA and FAACT assessments not completed at baseline can be completed on C1D1 as long as they are done before treatment begins.

⁸ PG-SGA and FAACT assessments should be completed within 4 (+/-2) weeks of completing or discontinuing neoadjuvant chemotherapy.

⁹ Follow-up for survival and disease progression will be done every 3-6 months years 1-3, every 6 months years 4-5, and every 12 months thereafter.

¹⁰ May be done by telephone in lieu of an in-person visit.

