7. TREATMENT PLAN

7.1 Treatment Dosage and Administration

Patients on this trial will be treated with neoadjuvant FOLFIRINOX for 2 cycles (1 cycle = 28 days). Patients will receive FOLFIRINOX on an outpatient basis on days 1 and 15 of each cycle. Following neoadjuvant treatment, patients will undergo repeat imaging (CT or MRI) to be reassessed for resectability of the tumor. Further adjuvant treatment will be determined at the treating physician's discretion (i.e. chemoradiotherapy or adjuvant chemotherapy). It is important to note that post-neoadjuvant therapy is determined by the treating physician per their institutional guidelines and standard of care. While this study will collect data regarding disease progression and survival from the post-neoadjuvant period, this protocol does not dictate post-neoadjuvant treatment which may be done at other institutions.

For patients with an R1 resection, any chemoradiotherapy will be included in the 24 weeks of perioperative therapy. Chemoradiotherapy and the timing in which it will be given will be determined at the treating physician's discretion based on margin status and the patient's recovery. Furthermore, patients who receive chemoradiotherapy may also receive adjuvant chemotherapy; however, this will be based on the treating physician's discretion. Recommended radiosensitization will be through 5FU 200 mg/m²/Day continuous infusions M-F of each week or capecitabine 825 mg/m² PO BID M-F for the duration of radiation therapy. Patients who

receive adjuvant therapy will receive treatment based upon treating physician's discretion with a recommended duration of therapy lasting 6 months accounting for preoperative therapy.

The neoadjuvant FOLFIRINOX regimen starting doses are: oxaliplatin 85 mg/m², followed by leucovorin 400 mg/m² given simultaneously with irinotecan 180 mg/m², followed by 5FU 400 mg/m² bolus and then 2400 mg/m² (Table 1). Patients require a PORT, PICC or other IV access to allow administration of 5FU via a continuous infusion pump. All agents should be administered within SOC drug administration guidelines. Appropriate dose modifications for each agent are described in Section 9.0. See drug monographs/package inserts for full details on each agent.

Agent	Dose*	Route	Schedule
Oxaliplatin	85 mg/m ² in 250 cc D5W	IV before irinotecan	Day 1,15 of each 28 day cycle

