9.2 Surgical Resection

Approximately 4 weeks (+/- 2 weeks) after the completion of the neoadjuvant treatment, patients will undergo standard of care operative exploration and complete extirpative surgery. Operative planning will be based on the original review of the patients' initial (i.e. pre-treatment) staging CT or MRI scan and the scan obtained after completion of the neoadjuvant protocol. All patients will undergo two modalities of operative exploration for occult metastatic disease undetectable with conventional cross-sectional imaging. Prior to laparotomy, patients will undergo a formal two-port staging laparoscopy to exclude the presence of occult metastatic disease involving the liver or peritoneal surfaces. Suspicious nodules possibly representing metastatic disease will be biopsied to confirm a pathologic diagnosis of metastatic pancreatic adenocarcinoma. Proof of metastatic cancer (i.e. stage IV cancer) will exclude patients from operative resection of the primary pancreatic cancer. In the absence of metastatic disease detectable with staging laparoscopy, patients will undergo a formal laparotomy with abdominal exploration to exclude occult metastatic disease involving the peritoneal surfaces or liver.

In the absence of occult metastatic disease, patients will undergo the planned operative procedure to resect the primary pancreatic adenocarcinoma completely. Based on preoperative imaging,

patients will undergo either a pancreatoduodenectomy (PD) or distal pancreatectomy and splenectomy (DPS). PD will be performed for patients with head and/or neck of pancreas cancers. DPS will be performed for patients with body and/or tail of pancreas cancers. PD and DPS will be performed according to standardized techniques which are employed routinely at Indiana University Hospital.

All margins of resection will be sampled intraoperatively to ensure complete clearance. For PD, the neck of pancreas and bile margins will be reviewed with frozen section histopathologic analysis. For DPS, the proximal pancreatic margin (i.e. body or neck of pancreas) will be reviewed intraoperatively. Final margin status (R0 versus R1) of the resected specimens will be recorded in addition to the intraoperative margin status assessments.

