11.3 Evaluation of best overall response

The best overall response is the best response recorded from the start of the treatment until disease progression/recurrence (taking as reference for PD the smallest measurements recorded since the treatment started). The patient’s best overall response assignment will depend on the findings of both target and non-target disease and will also take into consideration the appearance of new lesions.

Target Lesions	Non-Target Lesions	New Lesion?	Best Overall Response
-----------------------	---------------------------	--------------------	------------------------------

Protocol Version Date:
October 2, 2019

CR	CR	No	CR
CR	Non CR/ Non PD	No	PR
CR	Not evaluated	No	PR
PR	Non-PD or not all evaluated	No	PR
SD	Non-PD or not all evaluated	No	SD
Not all evaluated	Non-PD	No	NE
PD	Any	Yes or No	PD
Any	PD	Yes or No	PD
Any	Any	Yes	PD

Patients with a global deterioration of health status requiring discontinuation of treatment without objective evidence of disease progression at that time should be classified as having “symptomatic deterioration”. Every effort should be made to document the objective progression even after discontinuation of treatment.

In some circumstances it may be difficult to distinguish residual disease from normal tissue. When the evaluation of complete response depends on this determination, it is recommended that the residual lesion be investigated (fine needle aspirate/biopsy) to confirm the complete response status.

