14.3 Statistical analysis plan

Primary Outcome:

- Pathologic complete response: the proportion of the 48 patients having a pathologic complete response with a 95% confidence interval (using normal approximation) will be calculated.

Secondary Outcomes:

- *Safety:* Adverse events of grades 3, 4, 5 by the CTCAE v4.3 criteria for each category listed in section 2.1.6 will be summarized. The proportion of patients with each category of AE will be calculated with a 95% confidence interval. After the enrollment of the first 20 patients, we will evaluate the rate of surgical resection. If >6 patients are not able to proceed with surgery due to excessive toxicity or progression (not including occult metastatic peritoneal disease that was found during surgery and not on imaging) the study will discontinue due to unacceptable toxicity.

- *Ability of patients to undergo surgical resection after receiving neoadjuvant FOLFIRINOX*: the proportion of patients who are able to go through surgery among those who have resectable tumor will be calculated accompanied with a 95% confidence interval.
- *Rate of resectability* will be evaluated by determining the proportion of patients who are able to undergo surgery with resection of their primary tumor (R0 vs R1) resection. A 95% confidence interval will be constructed for the rate.
- *Disease free survival (DFS)*: DFS is defined as time from registration to evidence of tumor recurrence (including clinical deterioration related to the underlying pancreatic cancer, as assessed by the investigator) or death from any cause. Kaplan-Meier curve for DFS will be plotted. Median DFS time will be calculated accompanied with a 95% confidence interval.
- *Overall survival*: time from registration to death for 48 patients with right censoring will be analyzed using Kaplan-Meier estimate. Median survival time will be obtained accompanied with a 95% confidence interval.
- *Objective response rate*: proportion of patients with complete responses (CR) or partial responses (PR) after 4 cycles of FOLFIRINOX treatment will be constructed with a 95% confidence interval.
- *Disease control rate*: Proportion of patients with complete responses (CR), partial responses (PR), or stable disease (SD) after 4 cycles of FOLFIRINOX treatment will be obtained with a 95% confidence interval.

Tertiary Outcomes:

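### Calendar footnote 5 can be read as making the post-FOLFIRINOX scan discretionary, against 7.1 and 9.2, and 14.3 gives ORR and DCR no rule for unscanned patients

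*Combined protocol and SAP*

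**What the plan says.** **The scan.** Section 7.1 states it for everyone: "Following neoadjuvant treatment, patients will undergo repeat imaging (CT or MRI) to be reassessed for resectability of the tumor". Section 9.2 takes its existence for granted, basing operative planning on the initial staging scan and "the scan obtained after completion of the neoadjuvant protocol". In the Section 10 calendar, the CT/MRI row has one mark between baseline and long-term follow-up, in the surgical evaluation/end-of-treatment column. Footnote 5 on that mark reads "Repeat imaging may be performed prior to surgical resection at the treating physician's discretion". Later imaging is not a fixed response assessment. Footnote 4 says "Disease progression will be assessed via radiology report from any MRI or CT scans done during the follow-up period per standard of care".

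**The endpoints.** ORR and DCR are secondary objectives in 2.2. Section 14.3 defines ORR as the "proportion of patients with complete responses (CR) or partial responses (PR) after 4 cycles of FOLFIRINOX treatment" and DCR as the "Proportion of patients with complete responses (CR), partial responses (PR), or stable disease (SD) after 4 cycles of FOLFIRINOX treatment". It names no denominator for either. Section 7.1 gives two 28-day cycles with treatment on days 1 and 15, which makes four treatments. Section 11.3.1 makes a patient with no imaging not evaluable at that time. Section 14.2 requires a post-baseline assessment (or death before any evaluation) for the efficacy set, without saying what kind of assessment.

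**The stopping rule.** Section 14.3 counts patients in the first 20 who cannot proceed to surgery because of toxicity or progression, "not including occult metastatic peritoneal disease that was found during surgery and not on imaging". Section 14.4 applies the same threshold of more than 6 patients to toxicity alone.

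**The concern.** The end-of-treatment scan is the only planned RECIST assessment between baseline and surgery. Once the primary tumour is out, its response to FOLFIRINOX can no longer be measured. A scan missed in a resected patient is therefore lost for good.

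If scanning is left to the physician, the scanned patients need not represent the cohort. Scans might be ordered mainly when progression is suspected, or mainly when resectability is in doubt. The documents do not say which, so the direction of any bias is unknown.

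The analysis text does not close the gap. Computing ORR among scanned patients and computing it among all patients, with not-evaluable counted as non-response, are both consistent with 14.3. The first is open to selection and the second to understatement. The choice could be made after the data are seen.

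A narrower second issue concerns stopping. Under 14.3, peritoneal metastases found at operation in a patient who had no preoperative scan literally satisfy the exemption, because they were found at surgery and not on imaging. Nothing there says that a scan must have been done.

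**Working it through.** **1. The plan's own figure.** Section 14.1 states 82% power with 43 evaluable patients (48 × 0.90 = 43.2), pCR 1% against 10%, two-sided 5%. The exact binomial test rejects at 3 or more pCRs. P(X ≥ 3 | n = 43, p = 0.10) = 81.8%, with attained type I error P(X ≥ 3 | n = 43, p = 0.01) = 0.92%. The figure reproduces. pCR is read from the surgical specimen, so the scan has no bearing on it.

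**2. Do the passages conflict?** Side by side: 7.1 says the scan will happen, 9.2 uses it, and footnote 5 says repeat imaging may happen at discretion. Two features favour reading footnote 5 as a qualifier of the scan itself. It uses the same term, repeat imaging, that 7.1 uses for the post-treatment scan. The calendar's other footnotes of this kind (3 on pregnancy testing, 6 on sample collection, 10 on telephone contact) each qualify the mark they sit on.

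**3. What unscanned patients could do to ORR.** The documents give no scan rate and no expected ORR for this population. Assumptions: N = 43 (the evaluable number in 14.1), m patients scanned, and about 30% of those responding (r, rounded to whole patients). Then

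- observed ORR = r / m
- lowest all-patient ORR (no unscanned patient responded) = r / N
- highest all-patient ORR (every unscanned patient responded) = (r + N − m) / N

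| Scanned m | Responders r | Observed r/m | Lowest r/43 | Highest (r + 43 − m)/43 |
|---|---|---|---|---|
| 43 | 13 | 30.2% | 30.2% | 30.2% |
| 39 | 12 | 30.8% | 27.9% | 16/43 = 37.2% |
| 32 | 10 | 31.3% | 23.3% | 21/43 = 48.8% |
| 26 | 8 | 30.8% | 18.6% | 25/43 = 58.1% |

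The observed rate barely moves from row to row while the range of possible true rates widens. Using all 48 enrolled gives similar ranges: 27.1% to 37.5% with 43 scanned, and 18.8% to 58.3% with 29 scanned.

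For DCR, assume about 85% control among those scanned. With N = 43 the ranges are 33/43 = 76.7% to 37/43 = 86.0% (39 scanned), 27/43 = 62.8% to 38/43 = 88.4% (32 scanned), and 22/43 = 51.2% to 39/43 = 90.7% (26 scanned).

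These are outer limits, not estimates of bias. They vanish when everyone is scanned.

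**4. The stopping count.** More than 6 of 20 means at least 7. By finding, for an unscanned patient who does not have the primary resected:

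| Found at surgery | 14.3 | 14.4 |
|---|---|---|
| Peritoneal metastases | Can be left out as occult | Not counted (toxicity only) |
| Liver metastases or local progression | Counted as progression | Not counted (toxicity only) |

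The scan can change the count only in the top-left cell. The documents give no rate of peritoneal disease found at surgery and no scan rate, so the size of the shift cannot be derived.

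**The case against.** **Footnote 5 may only permit an extra scan.** On this reading the calendar mark requires the end-of-treatment scan, and the footnote allows another one nearer surgery. This is tenable, and it agrees with 7.1 and 9.2. The shared term and the way the neighbouring footnotes work make it the weaker reading, but it cannot be excluded. The finding is therefore that the footnote can be read as discretionary, not that the plan abandons the scan. The text needs reconciling on either reading.

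**The plan already handles missing scans.** Section 11.3.1 does supply the not-evaluable status. It does not say whether those patients stay in the denominator, and neither does 14.3.

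**A postoperative scan could be scored as complete response.** A reader might infer this from 11.3, where "The best overall response is the best response recorded from the start of the treatment until disease progression/recurrence". The documents do not support it as a likely outcome. Section 14.3 ties ORR to response after FOLFIRINOX rather than to follow-up scans, and 11.4.3 requires initially raised markers to normalise before CR. It remains sensible to exclude postoperative scans explicitly, because the cycle count in 14.3 does not identify the end-of-treatment scan.

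**Progression missed for lack of a scan escapes the stopping rule.** A reader might infer this in general. The 14.3 exemption covers only peritoneal disease found at surgery, and 9.2 describes occult disease as what cross-sectional imaging cannot detect, so an unscanned patient does not clearly qualify. Nor can the background rates in 1.3 be turned into 2 to 3 of the first 20 patients (3/21 × 20 = 2.9; 2/16 × 20 = 2.5). One rate is progression on treatment in borderline or locally advanced disease, the other comes from a different regimen, and neither is specific to the peritoneum.

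**These are minor endpoints.** ORR and DCR are in 2.2 and 14.3 but not among the outcome measures in 3.2. That limits the importance of the point without removing it.

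**Conclusion.** The point holds as an inconsistency with a real consequence for two secondary endpoints. Footnote 5 can be read against 7.1 and 9.2. If it is followed, ORR and DCR can come from a physician-selected subset, with no stated rule for the rest and a cycle count in 14.3 that does not match 7.1.

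The size depends on a scan rate the documents do not give. Assuming 43 patients and about 30% response among those scanned, the possible all-patient ORR is 28% to 37% with 39 scanned, 23% to 49% with 32, and 19% to 58% with 26.

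The stopping issue is secondary. It is confined to peritoneal disease under the 14.3 wording, does not arise under 14.4, and is of unknown size. A reader might also infer that the primary result is at risk. It is not: pCR comes from the specimen, and the stated 82% power reproduces and is unaffected.

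**What to change.** - Reconcile footnote 5 with 7.1 and 9.2 so that all three say the same about the end-of-treatment scan. If footnote 5 was meant to allow an additional scan, say so there.
- In 14.3, define ORR and DCR on the preoperative scan at the end of neoadjuvant treatment, in the cycle terms of 7.1 (2 cycles, 4 treatments), and exclude scans after resection.
- State the denominator. Keep patients without that scan in it as non-responders (for DCR, as not controlled), and report their number.
- Reconcile the stopping wording of 14.3 and 14.4, including whether progression counts and whether the imaging exemption presupposes that a preoperative scan was done.

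The cost is a calendar footnote and a few sentences of analysis text. Sample size and power do not change, and 7.1 and 9.2 already describe the scan. The downside is that ORR and DCR may read slightly lower, because unscanned patients stay in the denominator.

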12.2 Blood Collection

Blood samples for future, yet undetermined, research studies (in addition to the blood samples taken as part of standard of care) will be collected prior to treatment (i.e. at baseline or C1D1 as long as completed before treatment begins) whenever possible and at the time of surgical evaluation (i.e. 4 weeks [+/-2 weeks] post neoadjuvant chemotherapy). These blood samples will be stored in the IUSCC Tissue Bank or IU CTSI Specimen Storage Facility.

Please refer to the study laboratory manual for complete instructions regarding tissue collection, processing, transfer and storage.

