Handling and Disposal

To minimize the risk of dermal exposure, always wear impervious gloves when handling vials containing 5FU. This includes all handling activities in clinical settings, pharmacies, storerooms, and home healthcare settings, including during unpacking and inspection, transport within a facility, and dose preparation and administration. If a solution of 5FU contacts the skin, wash the skin immediately and thoroughly with soap and water. Procedures for proper handling and disposal of anti-cancer drugs should be considered.

Adverse Events

The most common toxicities seen with 5FU therapy include stomatitis, esophagopharyngitis (which may result in sloughing and ulceration), diarrhea, anorexia, nausea and vomiting. Neutropenia commonly follows treatment with white count nadir observed between days 9 and 14 following therapy. Mild alopecia has been reported, though is usually not complete. Dermatitis, in the form of a pruritic maculopapular rash that usual appears on the extremities and (less frequently) trunk, is generally reversible and responsive to symptomatic treatment. This dermatitis may be increased with sun exposure.

Other less common adverse reactions are:

Hematologic: pancytopenia, thrombocytopenia, agranulocytosis, anemia.

Cardiovascular: myocardial ischemia, angina.

Gastrointestinal: gastrointestinal ulceration and bleeding.

Allergic Reactions: anaphylaxis and generalized allergic reactions.

Neurologic: acute cerebellar syndrome (which may persist following discontinuance of treatment), nystagmus, headache.

Dermatologic: dry skin; fissuring; photosensitivity, as manifested by erythema or increased pigmentation of the skin; vein pigmentation; palmar-plantar erythrodysesthesia syndrome, as manifested by tingling of the hands and feet followed by pain, erythema and swelling.

Ophthalmic: lacrimal duct stenosis, visual changes, lacrimation, photophobia.

Psychiatric: disorientation, confusion, euphoria.

Protocol Version Date:
October 2, 2019

Miscellaneous: thrombophlebitis, epistaxis, nail changes (including loss of nails)

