14.2 Analysis datasets

Population	Definition
Enrolled	This will comprise all patients who meet the eligibility criteria and are registered onto the study.
Efficacy Evaluable	This will comprise all patients who complete at least 2 treatments and either undergo at least one post-baseline assessment or die before any evaluation.
Not Evaluable for Efficacy	This will comprise of patients who do not complete 2 out of 4 treatments unless it is related to profound toxicity leading to treatment discontinuation.
Safety	This will comprise all patients that contribute data to the safety analysis. This population should be specifically defined in the protocol.

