18.2 Adverse Event (AE) Reporting

Adverse events (AEs) will be recorded from the time of first study drug administration and for at least 30 days after treatment discontinuation, regardless of whether or not the event(s) are considered related to trial medications. All AEs considered related to trial medication will be followed until resolution, return to baseline, or deemed clinically insignificant, even if this occurs post-trial.

18.2.1 Reporting to the Data Safety Monitoring Committee (DSMC):

Regardless of study sponsorship, the DSMC chair and/or coordinator will review all expedited SAE reports through OnCore®. Expedited reports are completed per IRB guidelines and may include the IRB Prompt Reporting form, and/or non-compliance form. Submission of this information to the DSMC is **additional to** any other protocol-specified regulatory bodies (e.g. FDA, pharmaceutical company) to be notified. When follow-up information is received, a follow-up report should also be created in OnCore®. The DSMC chair and/or coordinator will review expedited SAE reports monthly.

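### The calendar requires no safety laboratory test after the last FOLFIRINOX dose, so laboratory AEs after that dose are captured only through routine care

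*Combined protocol and SAP*

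**What the plan says.** Section 7.1 plans two 28-day cycles: "Patients will receive FOLFIRINOX on an outpatient basis on days 1 and 15 of each cycle". That makes four doses, and Section 14.2 uses the same count when it defines the non-evaluable group: "This will comprise of patients who do not complete 2 out of 4 treatments".

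The calendar in Section 10 marks physical examination, BP and weight, ECOG status, complete metabolic panel, creatinine clearance, and platelets/ANC/Hgb at baseline and on D1 and D15 of cycles 1-2. All of these rows are blank in the Surgical Evaluation/EOT column. That column holds the AE and concomitant medication check, imaging, resection, research tissue and blood, and the two questionnaires. Footnote 10, attached to the AE and medication cell, reads: "May be done by telephone in lieu of an in-person visit". Footnote 2 gives every patient a routine surgical evaluation visit 4 (+/-2) weeks after chemotherapy and adds: "Information collected during this visit will be used for the EOT visit for this study". It names no test.

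Section 8 ties toxicity assessment to this calendar. Section 18.1.1 counts an abnormal laboratory finding as an AE, and Section 18.2 sets the window: "Adverse events (AEs) will be recorded from the time of first study drug administration and for at least 30 days after treatment discontinuation". Section 14.3 plans the proportion of patients with each category of grade 3-5 AE, with 95% confidence intervals. Section 15 says that only selected standard-of-care data enter OnCore.

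**The concern.** After doses 1 to 3, the laboratory effects of one dose are looked for at the next dosing visit. The last dose has no next dosing visit. The AE window stays open for 30 days, but no safety laboratory test is scheduled in it, and a conversation, by telephone or in person, does not detect a low neutrophil count or a raised bilirubin.

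Describing the AEs of preoperative FOLFIRINOX is the first secondary objective (Section 2.2), and the rationale (Section 1.4) offers safety information for this setting as one of the study's contributions. If laboratory events after the last dose are ascertained differently from those after earlier doses, the per-patient proportions tend to be too low. Whether they are then depends on local habits of testing and abstraction, which a reader of the results cannot see.

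**Working it through.** **1. Count the doses.** 2 cycles x 2 doses = 4, which agrees with the four treatments in Section 14.2.

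**2. Match tests to doses.** The required tests fall on the four dosing days, so the test that follows dose k is the one taken at dose k+1. Doses 1, 2 and 3 have one; dose 4 has none. Uncovered share = 1/4 = 25%. For a patient who stops after three doses, with no further dosing-day visit, it is 1/3; after two, 1/2. The +/-7 day window moves the D1 and D15 visits but does not create another one.

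**3. Time without a required test.** The surgical evaluation falls 4 (+/-2) weeks after completion. If completion means the last dose, the gap is 14 to 42 days. If it means the end of the second 28-day cycle, about 14 days after dose 4, the gap is 28 to 56 days. The documents do not say which.

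**4. Compare with the nadir.** The 5FU adverse event text in Section 13 says: "Neutropenia commonly follows treatment with white count nadir observed between days 9 and 14 following therapy". A test at the next dose, nominally 14 days later, falls at the end of that range for doses 1 to 3. After dose 4, even the earliest surgical evaluation (day 14) only reaches the end of the range, and a typical one (day 28) is two weeks past it.

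**5. Illustrate the possible shortfall.** The documents give no per-dose risk for this regimen, so the risk q is an assumption. Assume also that q is equal and independent across doses, that every event after doses 1-3 is found, and that none is found after dose 4. Then:

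- true patient incidence = 1 - (1 - q)^4
- captured incidence = 1 - (1 - q)^3

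| Assumed q | True | Captured | Difference (points) | Patients out of 48 |
|---|---|---|---|---|
| 5% | 18.5% | 14.3% | 4.3 | 2.1 |
| 10% | 34.4% | 27.1% | 7.3 | 3.5 |
| 15% | 47.8% | 38.6% | 9.2 | 4.4 |

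The relative shortfall is about 23%, 21% and 19% (for example 0.0429/0.1855 = 0.231). Zero detection after dose 4 is the extreme case, so for a given q these differences are upper bounds on what is lost there.

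**The case against.** The best defence is that routine care fills the gap. Every patient has a surgical evaluation visit, and its information is used for EOT. Section 12.2 describes the research blood as taken "in addition to the blood samples taken as part of standard of care", so other blood tests are expected. An abnormality found in the window must be recorded as an AE whatever its attribution, and related AEs are followed to resolution. This stands in part: a reader might infer that laboratory toxicity after dose 4 is not recorded at all, or that patients reach surgery with nobody having looked at their counts, and the documents support neither. What remains is that no test is named and only selected standard-of-care data are promised in OnCore, so capture is possible but not systematic. The EOT research blood is stored and is not a safety test.

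Second, a reader might take the 4-9 points as the size of the bias. They are not. Table 4 lowers doses or stops agents after severe toxicity, patients prone to toxicity tend to have had a first event already, and routine tests will find some events. Each of these shrinks the difference. Nor is perfect detection after doses 1-3 realistic, with one scheduled test each.

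Third, a reader might infer that nothing physical is assessed at EOT. The PG-SGA is due then and brings a patient-reported weight and a clinician's nutritional examination (Section 12.3.1, Appendix IV). What is missing is the protocol physical examination and measured BP and weight.

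Fourth, a reader might see footnote 10 as the cause. It covers only the AE and medication cell and releases no laboratory test, because none is marked there.

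**Conclusion.** The gap is real and limited. After the last dose (dose 4 of 4 as planned, or the last dose received in patients who stop early) the calendar requires no blood count, metabolic panel, protocol physical examination or measured BP/weight. Laboratory AEs after that dose are captured only if routine care tests for them and the result is abstracted.

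Grade 3-5 laboratory AE proportions may therefore be understated. The direction follows from the schedule. The size cannot be estimated from the documents, because it depends on per-dose risks and routine testing that they do not report; the tabulated differences are illustrative upper bounds under the stated assumptions. The firm figure is the planned-course share: one dose in four has no later required safety laboratory test.

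Only a descriptive secondary safety summary is affected. The primary endpoint, sample size, power and type I error do not depend on it. This is a cheap improvement worth making, not a flaw that threatens the trial's main conclusion.

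**What to change.** In the Surgical Evaluation/EOT column of Section 10, mark the existing rows for platelets, ANC and Hgb and for the complete metabolic panel, plus measured weight and ECOG status if these are recorded at the visit. State that routine results satisfy them.

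State also that all counts and chemistries obtained in routine care from the last dose through the 30-day AE window are entered in OnCore. Abstracting only the value closest to surgery would not be enough, since it is usually taken well past the day 9-14 nadir. With both changes, 4 of 4 planned doses are followed by a required test instead of 3 of 4. Footnote 10 needs no change.

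The cost is a calendar amendment, a little data entry, possibly one blood test added to the existing EOT research draw in patients who do not go to surgery, and slightly higher reported AE rates. The change secures persistent abnormalities. Transient nadirs will be seen only where a routine count was taken, and the safety report should say so. This concerns data capture only and alters no treatment or surgical decision rule.
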